13.1.2. Appendix B Instructions for Use

Instructions for Use

The test product combines whole food sourced Vitamin C, quality Echinacea, Ivy Extract, Zinc, Ginger and Turmeric. This formula is designed to support the immune system while soothing & clearing cough, with the main active components of Echinacea fresh pressed juice, Ivy Extract and Zinc

Daily Dosage:

1 Packet contain: Active Ingredients: Echinacea, Ivy Extract, Camu Camu, Ginger, Turmeric, Zinc

Inactive Ingredients: Natural Flavor, Guar Gum, Monk Fruit Sweetener, Citric Acid

Serving Size 1 Sachet (5.4g)		
Servings per Container 3		
	Amount Per Serving	% Daily Value
Calories	5	
Total Carbohydrate	1 g	<1%
Total Sugars	<1 g	†
Vitamin C (as Camu-camu (Fruit) Powder & Ascorbic Acid)	500 mg	833%
Zinc (as Zinc Gluconate)	15 mg	100%
Organic Turmeric Powder (Rhizome)	500 mg	†
Echinacea purpurea Extract (Aerial)	400 mg	†
Organic Ginger Powder (Root)	250 mg	†
English Ivy Extract (Leaf)	25 mg	†

OTHER INGREDIENTS: Natural Flavor, Guar Gum, Monk Fruit Extract, Citric Acid

Directions: Mix 1 packet with 6-8 oz of hot water at the onset of symptoms and repeat twice a day, 4-6 hours apart, for the duration of your cold symptoms.

*These statements have not been evaluated by the Food and Drug Administration. This product is not intended to diagnose, treat, cure or prevent any disease.

13.1.3. Appendix C Screening Form

Screening

- 1. Are you at least 18 years old? (DOB?) (Y/N)
- 2. Have you ever been diagnosed with any chronic liver disease? (Y/N)
- 3. Have you ever been diagnosed with any chronic renal disease? (Y/N)
- 4. Are you pregnant or breastfeeding? (Y/N)
- 5. Do you have any allergies to any of the following? (Y/N)
 - a. Echinacea
 - b. Ivy Extract
 - c. Camu Camu
 - d. Vitamin C
 - e. Ginger
 - f. Turmeric
 - g. Zinc
 - h. Monk fruit
 - i. Guar Gum
 - j. Citric Acid
 - k. Natural Flavoring
- 6. Have you ever been diagnosed with an autoimmune or immunodeficiency disease? (Y/N)
- 7. Do you have more than 10 alcoholic beverages per week? (Y/N)
- 8. Are you willing to try the test product for relief of your symptoms? (Y/N)
- 9. Are you comfortable taking your own temperature with a digital thermometer? (Y/N)

13.1.4. Appendix D Baseline Form

Baseline

- 1. Demographics
 - a. Race/Ethnicity (Black or African American, White, Asian, American Indian or Alaska Native, Native Hawaiian or another pacific islander, other: _____, do not want to share)
 - b. Sex (M, F, or Do not want to share)
- 2. On average how many colds do you get a year?
- 3. On average How long do your colds usually last? (1-3 days, 4-6 days, 7-9 days, >10 days)
- 4. When you have a cold what Cold Symptoms do you usually experience? (check all that apply)
 - a. Cough
 - b. Hoarseness
 - c. Muscle aches
 - d. Runny Nose
 - e. Nasal Congestion
 - f. Scratchy Throat
 - g. Sore throat
 - h. Sneezing
 - i. Oral Temp > than 37.7 °C (99.9 °F)
 - j. Other:
- 5. Do you take any medication when you have a cold (i.e. Dayquil/Nyquil, Advil, or Prescription etc.)?
 - a. If so, which medications do you take?
 - b. How often do you normally take them? (once a day, as needed, or as instructed)
 - c. Are they successful in treating your symptoms?
- 6. Do you take any supplements when you have a cold (Emergen-C, Vitamin C, Airborne, Nettipot, etc.)?
 - a. If so, which supplements do you take?
 - b. How often do you take the supplement when you have a cold? (once a day, several times a day, every other day, once in a while)
 - c. Are they successful in helping with your symptoms?

13.1.5. Appendix E Symptom Diary

Daily Symptom Survey

BEFOREtaking the test product OR any allowed medication, please answer all of the following questions daily for the duration of your cold symptoms.

REMINDER: DURING THE TRIAL, YOU ARE NOT ALLOWED TO TAKE ANY COLD MEDICATIONS (NYQUIL/DAYQUIL, TYLENOL COLD, COUGH SYRUP/LOZENGES, ETC.)

1. Cough			
0	1	2	3
No Symptom	Slight	Moderate	Severe
2. Hoarseness			
0	1	2	3
No Symptom	Slight	Moderate	Severe
3. Muscle aches			
0	1	2	3
No Symptom	Slight	Moderate	Severe
4. Runny Nose			
0	1	2	3
No Symptom	Slight	Moderate	Severe
5. Nasal Congestion			
0	1	2	3
No Symptom	Slight	Moderate	Severe
6. Scratchy Throat			
0	1	2	3
No Symptom	Slight	Moderate	Severe

7. Sore throat

0	1	2	3
No Symptom	Slight	Moderate	Severe
8. Sneezing			
0	1	2	3
No Symptom	Slight	Moderate	Severe

- 9. Did you take any pain/fever reducer (ibuprofen/acetaminophen today? (Y/N)
 - a. Why?
 - b. Did it work? (Y/N)
- 10. Have you taken any other cold medications (Nyquil, Dayquil, other cold medication, cough drop, cough syrup, etc.)? (Y/N)
 - a. If yes, please exit from the study
- 11. Have you seen a doctor for your symptoms? (Y/N)
 - a. If yes, were you prescribed anything? $(Y/N) \rightarrow$ if yes please exit from the study
- 12. Did you experience any side effects after taking the product? (Y/N)
 - a. If yes, please fill out the Adverse Event form.

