2.2.3. Minimization of Risks

Research participants will be carefully screened to meet enrollment criteria. Participants meeting exclusion criteria will not be enrolled. The study participant informed consent will be presented with clear description of the study requirements and opportunity to have questions answered before enrollment will be provided. Once an event occurs, review of symptoms will be

ascertained daily until symptoms have resolved or for 18 days. Reporting of adverse events will be reviewed routinely and in accordance with regulatory guidelines (21CFR, GCP) by the Principal Investigator. Participants with occurrence of worsening symptoms or adverse events will be advised to stop the product and may seek medical attention and exit the study.

3. Study Objectives

The purpose of the present study is to evaluate 1) the impact of the Immune Support test product on the duration of symptoms of the common cold in adult participants and 2) the subjective experience of these participants related to general health, common cold symptoms, and personal experience with the product. [13, 18, 29, 32]

This will be evaluated based on the primary and secondary endpoints. These endpoints, the analysis populations, and their respective measures are described below. Further details on the methods for measuring the outcomes can be found in the Study Outcome Measures and Analysis Plan sections.

Primary Endpoint:

The primary endpoint will be time to freedom from cold symptoms, with the clock starting at the onset of the cold. Where the onset is defined as the point in time when the participant experiences 2 or more cold symptoms. The primary analysis will be a Kaplan-Meier analysis of time to absence of all symptoms, based on the participants' self-report. There is no control group for the primary analysis. [5]

Secondary Endpoint:

- Secondary endpoints involve the duration and severity of the separate cold symptoms.
- Comparison against the participant's normal behavior.
- Net Promoter Score.
- Adverse events will be summarized.
- An additional data presentation will consist of results from both Treatment and Control in similar studies appearing in the literature. There will be no formal statistical comparison of results from this study and historical studies.

4.Study Design

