The present study will be a single site, prospective, single arm observational study of minimal risk consisting of at least 200 participants who suffer from cold symptoms. The participants must meet additional inclusion/exclusion criteria (see Inclusion/Exclusion Criteria). Participants will begin taking the powder drink-mix at the onset of their cold symptoms. Onset is defined as the point in time the participant experiences 2 or more cold symptoms (cough, hoarseness, muscle ache, nasal drainage,

nasal congestion, scratchy throat, sore throat, sneezing, or an oral temperature greater than 37.7 °C (99.9 °F)). When the participant experiences 2 or more symptoms, they will report symptoms in the cold start form. If they meet the criteria for a cold, they will start completing the daily cold symptom diary prior to taking the test product. After consuming the product, the participant will complete the cold symptom diary daily until all symptoms resolve. Since none of the ingredients in the test product have been seen to provide relief from fever or pain, the participant will be allowed to take a pain reliever and fever reducer (e.g. ibuprofen or acetaminophen). If medication is taken, the participant will record this in their symptom diary.

Study enrollment and management will be decentralized, where participants do not visit an investigator or a clinic for clinical assessment. The participants will participate in the study at home. All data collected from during this study will be reported by the participant via eCRFs, eDiary, and other electronic data entries. If a visit is required, it will be conducted via remote contact by telephone.

4.1.Test Product

Overview:

Participants in this study will consume the test product twice a day (4-6 hours apart) at the onset of cold symptoms. The participant will mix one packet of the test product in 6-8 ounces of water. The test product will be delivered to the participants' residence in a single shipment consisting of an18-day supply (36 packets) of the test product. The study participant will mix the contents of the packet into 6-8 oz. of hot water and drink twice a day during the duration of the cold.

Below is the description of the test product and its ingredients.

Test Product

Description: Combining whole food sourced Vitamin C, Echinacea, Ivy Extract, Zinc, Ginger and Turmeric. This formula is designed to support the immune system while reducing the duration of cold.

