4.3. Participation Period

Participants are expected to participate in the study for 18 days after the onset of the first cold. Onset is defined as the day that the participant experiences 2 or more cold symptoms. Participant will be exited once all symptoms have been resolved or at 18 days whichever is shorter. If no cold has started within 90 days of participant study start date (date the participant receives and records receipt of test product) participants will be exited from the study.

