- Participant will take the test product twice a day, at least 4-6 hours apart.
- The next day the participant will complete their symptom diary prior to taking the test product. Once completed they will mix 1 packet of the test product into 6-8 oz of water and consume the whole drink. They will take the test product again 4-6 hours later.
- The participant will complete this process daily until their cold symptoms resolve or for 18 days, whichever is shorter.
- If the participant takes ibuprofen or acetaminophen at any time, the participant will record this on their symptom diary.
- After taking the test product, the participant will be instructed to fill out an Adverse Event form for any side-effects experienced.
- The participant will be prompted, by email, to complete the study exit form once the participant's symptoms resolve completely or after 18 days, whichever is shorter.
- Neither the sponsor nor Hawthorne Effect, Inc. will make any attempt to collect any unused test product.
- Upon receipt of study exit survey and review of completed study forms, participant will receive an Amazon gift card of \$25 via email.

6.2.Study Schedule of Activities

Assessments	Screening	Consent	Before Receipt of Test Product	Product Received	Event Start Date**	Days 1-18*	Study Exit***
Study Window							
Screening Survey	Х						
Consent		Х					
Baseline Survey			х				
Demographics			х				
Acknowledgement of Receipt of Test Product				Х			
Test Product Consumed****					Х	Х	
Symptom Diary					Х	Х	Х
Meds & Supplements			Х				
AE Assessment					Х	Х	Х
Study Exit Survey							Х

^{*}Participant will participate in the study starting on the day of the cold until the cold symptoms resolve or 18 days whichever is shorter.

^{**} The day the participant experiences 2 or more of the protocol defined symptoms

^{***} The participant will exit the study at the time of complete cold symptom resolution, 18 days after the start of cold symptoms, or at 90 days if no cold is experienced by the participant.

^{****} The product will be consumed twice a day, 4-6 hours apart

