7.3. Analysis Plan

Time-dependent variable analysis

The primary analysis involves time dependent variables. The Kaplan-Meier algorithm will be used to analyze time to freedom from cold symptoms. Data presentation will include tables and graphs; in particular tables of participants at risk at various time points.

Censoring:

- Participants who do not have a cold during the trial will not be in the ITT population, and will
 not be included in the endpoint analysis.
- Participants who report the onset of a cold, but who do not complete the daily reports through
 18 days will be censored as of the date of the last report.
- Participants who still have cold symptoms at 18 days will be censored at that time.
- Participants will also be censored if they withdraw from the trial.

Secondary Endpoints:

- Analysis of the individual cold symptoms will be a presentation of median time until the
 individual symptom resolves. The median for this purpose is the value computed as part of
 the Kaplan-Meier algorithm.
- An additional analysis will investigate the relation between baseline age and gender, and the time to resolution.
- Adverse events will be summarized.
- An additional data presentation will consist of side by side presentation of results from both

Treatment and Control in similar studies appearing in the literature. There will be no formal statistical comparison of results from this study and historical studies.

General statistical methods:

Data will be analyzed using standard statistical methods, as further specified in a statistical analysis plan (SAP), which will be prepared in detail at a later date. [23]

- Data analysis will largely consist of summary statistics and graphs. The only formal statistical comparisons will be in covariate analyses.
- For continuous variables data presentation will consist of means, confidence intervals computed using the *t*-statistic, medians, and interquartile ranges. Group comparisons will use *t*-tests or ANOVA.
- For discrete variables confidence intervals will use the exact intervals, where available. Group comparisons will use Fisher's exact test, with the Monte Carlo version used where computationally necessary.
- For time to event variables analysis will use the Kaplan-Meier algorithm, and group comparisons will use the log-rank or proportional hazards methods, depending on the data type.
- Covariate analyses will investigate the relation between baseline and outcome variables, using

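### The Section 7.3 censoring rule, as worded, censors participants who recover and stop the diary as instructed, so almost no primary events would remain

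*Combined protocol and SAP*

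**What the plan says.** **When reporting stops.** Five parts of the protocol end reporting or participation at resolution, or at day 18 where a limit is given.

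- Section 2.2.3: symptoms are to be "ascertained daily until symptoms have resolved or for 18 days".
- Section 4: "the participant will complete the cold symptom diary daily until all symptoms resolve".
- Section 4.3: "Participant will be exited once all symptoms have been resolved or at 18 days whichever is shorter".
- Section 6.1, on the daily diary-and-product sequence: "The participant will complete this process daily until their cold symptoms resolve or for 18 days, whichever is shorter".
- Section 6.2, footnote to the schedule: "The participant will exit the study at the time of complete cold symptom resolution".

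The form in Appendix E agrees: "BEFOREtaking the test product OR any allowed medication, please answer all of the following questions daily for the duration of your cold symptoms".

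**Who is censored.** Section 7.3 has a bullet that begins "Participants who report the onset of a cold, but who do not complete the daily reports through". It sets day 18 as the limit and censors this group at their final entry. The neighbouring bullets censor participants who are still symptomatic at day 18 and those who withdraw.

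**The event.** Section 7.1 makes the primary analysis a Kaplan-Meier analysis of time to self-reported absence of all symptoms. Section 7.3 leaves further detail to a statistical analysis plan to be prepared later.

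**Pain/fever reducers.** Sections 4 and 6.1 require any use to be recorded in the diary, and Section 6.1 says this applies whenever a dose is taken. Item 9 of Appendix E asks about use today only.

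**The concern.** A participant who follows the instructions and recovers before day 18 will not have daily reports running to day 18. The incomplete-report bullet then applies to that person and, on its wording, turns the event into a censored time. The Kaplan-Meier curve is the primary result. It has no concurrent control and will be set beside published treatment and control arms. Whether recovered participants are events or censored therefore decides what the curve shows.

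The recording of the event raises a related gap. Appendix E asks for entries only while symptoms last, so it is unclear whether a participant who wakes symptom-free makes an entry at all. The Section 6.2 schedule marks a diary at study exit, but no text says that this entry must show absence of symptoms. The exit form in Appendix F does not ask whether symptoms are present or when they ended. Without a symptom-free entry, the last report is a symptomatic one and the event has no recorded date.

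A smaller mismatch lies in item 9. The entry is to be made before any allowed medication, so a dose taken later that day is outside that entry, and the next entry again asks only about its own day.

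**Working it through.** **1. The plan's own figure.** Section 7.2 expects 40% of 200 enrolled participants to have a cold: 200 × 0.40 = 80. This reproduces and is the number of colds used below.

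**2. One participant traced through the text.** All symptoms resolve on day 7, and the participant reports this and stops, as Sections 4, 4.3 and 6.1 direct. The last report is on day 7 and there are no reports for days 8 to 18. Under the incomplete-report bullet of Section 7.3 the participant is censored on day 7. The only participant with a cold who escapes every censoring bullet is one who reports daily to day 18 and is first symptom-free on day 18.

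**3. Expected events.** The documents give no distribution of cold duration, so these inputs are assumptions: Weibull durations with shape 2, median M of 5, 7 or 9 days, times rounded up to whole days, no dropout, and everyone stopping at resolution. The proportion still symptomatic after day t is

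S(t) = 0.5^((t/M)²).

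Events under the wording of Section 7.3 = 80 × [S(17) − S(18)].

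Events if resolution by day 18 counts = 80 × [1 − S(18)].

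| Median M | S(17) | S(18) | Resolved before day 18 | Events, Section 7.3 as worded | Events, resolution counted |
|---|---|---|---|---|---|
| 5 | 0.00033 | 0.00013 | 99.97% | 80 × 0.00021 = 0.02 | 80 × 0.99987 = 80.0 |
| 7 | 0.0168 | 0.0102 | 98.3% | 80 × 0.0065 = 0.5 | 80 × 0.9898 = 79.2 |
| 9 | 0.0843 | 0.0625 | 91.6% | 80 × 0.0218 = 1.7 | 80 × 0.9375 = 75.0 |

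For M = 7, for example, (17/7)² = 5.898 and 0.5^5.898 = 0.0168.

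**4. Effect on the curve.** No event can occur before day 18, so the estimate stays at 100% symptomatic through day 17 for every M. Counting resolution as the event recovers medians of 5, 7 and 9 days.

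**5. Sensitivity to the assumed shape.** A separate simulation used shapes of 1.0 and 1.5, medians of 4, 6, 8 and 10 days, and 500 trials of 80 colds per setting. It gave 0.07 to 2.2 events under the wording, against 57 to 80 when resolution is the event.

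**6. Item 9.** No arithmetic applies. With the entry completed before any dose that day, item 9 can only be answered no, although item 9b asks whether the dose worked. Use after the entry falls outside both that entry and the next.

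**The case against.** The strongest reply is that nobody would analyse the trial this way. The event is defined as absence of all symptoms, and censoring by its nature applies to people who have not had the event. The next bullet in Section 7.3 censors those still symptomatic at day 18, which presupposes that the others have resolved. The same section plans median times to resolution of each symptom, which makes little sense if recovered participants are censored. The later analysis plan can also settle the counting rule.

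Much of this stands. It makes the narrower reading, censoring only those who stop before resolution, the probable intent. A reader might infer from the table that the trial will produce an empty curve, and the documents do not support that forecast. What remains is that the narrower rule is not written. The day-18 bullet carries a symptom condition and the incomplete-report bullet does not. A later plan can fix the counting, but it cannot supply symptom-free entries that were never requested.

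A reader might also infer that reported durations will be too short, because no confirming entry or relapse rule is specified. The documents do not support this either. First absence of symptoms is a legitimate endpoint, and nothing in the documents gives a rate of premature symptom-free reports or of relapse.

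On item 9, participants may answer loosely or amend an entry later, and items 9b, 10 and 12 look backwards, which suggests that prior use was meant. The form does not say so.

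**Conclusion.** The contradiction is real and the wording of Section 7.3 needs correction. Applied as written alongside the stop-at-resolution instructions, it leaves about 0 to 2 events out of 80. That figure rests on the assumed Weibull shape and medians, and on everyone stopping at resolution. The conclusion depends little on the shape, because only a first symptom-free report on day 18 can count. The figure shows what the written rule does; it does not predict what a sensible analyst would report. The sample size is unaffected.

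The item 9 mismatch is a minor form fault. A reader might infer that it biases measured duration, but Section 7.3 plans covariate analyses of baseline medications only and none of on-study pain/fever reducer use. Its effect is limited to the reliability of the medication record.

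**What to change.** 1. Reconcile Sections 2.2.3, 4, 4.3, 6.1 and 6.2 and Appendix E with Section 7.3, and amend the censoring bullets. State that the first report of absence of all symptoms is an event on that date even if reporting then stops. State that censoring for incomplete reports or withdrawal applies only to participants who stop before reporting absence.
2. Say in Appendix E and Section 6.1 that the participant must make a symptom-free entry to record the event. This is data collection only. Section 6.1 ties each entry to product intake, so the documents should state how this entry relates to that sequence.
3. Reword item 9 along these lines: *Since your last diary entry, did you take any pain/fever reducer?*

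The cost is one amended rule, matching edits to the diary and exit text, one reworded item, and at most one extra electronic entry for a participant who would otherwise have stopped at the last symptomatic day. Items 2 and 3 should be in place before data are collected; item 1 should be settled before analysis.

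A confirming second entry, a relapse rule, a sustained-resolution sensitivity curve and an analysis discounting symptom-free entries after analgesic use are optional design choices. This point does not require them.

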- At time of enrollment, participant will be given access to the HIPAA compliant study portal.
 - The study portal provides access to study information, signed informed consent form, instructions for product use, frequently asked questions, study surveys, symptom diary, and data collection tools.
- Participant shall complete baseline assessments upon access to the portal.
 - Baseline assessment will include questions regarding the participants' demographics, medications, detailed information regarding previous colds, including treatment.
- To ensure that baseline assessments are completed before test product is used by the
 participant, study materials and study welcome package will be shipped to the participant once
 the clinical study manager/clinical operations coordinator confirms that the baseline assessment
 has been completed.
- The welcome package will include an information sheet that will outline instructions for their participation in the trial, the test product, disposable thermometer, and paper forms of the

- documents (paper form of study documents will be provided for real time data collection, in the event that the participant cannot log into the study portal to input data).
- Once the participant receives the test product, the participant will log into the study portal to acknowledge the receipt of the test product.
- Study start date will be the date of acknowledgement of receipt of test product.
- Participant will be sent weekly email reminders that remind them of their participation in the study. Once the participant indicates they are experiencing a cold. The participant will be reminded by email daily to complete their symptom diary.
- At the onset of their cold symptoms, the participant will complete the cold start form.
 - Onset is defined as the point in time the participant experiences 2 or more cold symptoms (cough, hoarseness, muscle ache, nasal drainage, scratchy throat, sore throat, sneezing, oral temperature greater than 37.7°C (99.9 °F)).
 - If fever is a symptom that the participant experiences, they will use the provided disposable thermometer to take their temperature and record it in the diary.
- If the participant meets all the criteria for a cold, they will start their symptom diary prior to taking the test product.
- After completing the surveys, the participant will take the test product. The participant will mix 1 drink-mix packet into 6-8 oz of water and consume the whole drink.

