7.1. Study Outcomes Measures

Analysis populations:

The *intent to treat* (ITT) population consists of all participants who are consented, report the onset of cold symptoms, and have taken the test product at least once. The primary analysis will be in the ITT population.

Primary Endpoint:

• The primary endpoint will be time to freedom from cold symptoms, with the clock starting at the onset of the cold. Where the onset is defined as the point in time when the participant experiences 2 or more cold symptoms. The primary analysis will be a Kaplan-Meier analysis of time to absence of all symptoms, based on the participant's self-report. There is no control group for the primary analysis.

Secondary Endpoints:

- Secondary endpoints involve the duration and severity of the separate cold symptoms.
- Comparison against the participant's normal behavior.
- Net Promoter Score.
- Adverse events will be summarized.
- An additional data presentation will consist of results from both Treatment and Control in similar studies appearing in the literature. There will be no formal statistical comparison of results from this study and historical studies.

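### Diary items 1–8 state no recall period, so a participant who rates only the moment before the first packet can be recorded as symptom-free too early

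*Combined protocol and SAP*

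**What the plan says.** - **Diary (Appendix E).** Before the product or any allowed medication, participants are to "please answer all of the following questions daily for the duration of your cold symptoms". Items 1–8 score eight symptoms from 0 to 3, and none names a reference period. The only day anchor is in item 9: "Did you take any pain/fever reducer (ibuprofen/acetaminophen today".
- **Timing (section 6.1).** After the first day, "The next day the participant will complete their symptom diary prior to taking the test product". The rating is therefore made once a day, ahead of that day's first packet.
- **Endpoint (section 7.1).** "The primary analysis will be a Kaplan-Meier analysis of time to absence of all symptoms, based on the participant's self-report". The clock starts at onset: "Where the onset is defined as the point in time when the participant experiences 2 or more cold symptoms". No length of absence and no confirming entry is required.
- **Exit (section 4.3).** "Participant will be exited once all symptoms have been resolved or at 18 days whichever is shorter".
- **Paper back-up (section 6.1).** For participants who cannot log in, "paper form of study documents will be provided for real time data collection".
- **Censoring (section 7.3).** Participants whose daily reports stop short of "18 days will be censored as of the date of the last report".

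**The concern.** Cold symptoms vary over the day. A person who coughs at night but is clear in the morning scores 0 if rating the moment and 1 or more if rating the past day. With no stated window both answers are correct, so the same illness can yield different event days in different participants.

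The effect has a direction. Compared with rating the past day, rating the moment can only bring the first all-zero entry forward. Sections 7.1 and 7.3 add no confirmation requirement, and section 4.3 ends participation at resolution, so a later symptomatic day would usually not be seen. Section 11 states that symptoms receive no medical review.

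At stake is the one quantity the study exists to describe. Section 7.3 plans a side-by-side display with published studies, including time to resolution of all symptoms. A curve shifted towards shorter colds would flatter the product in that display. The analyst cannot recover afterwards which window each participant had in mind.

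**Working it through.** **1. Does anything else on the form supply a window?**

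- Item 9 asks about a pain or fever reducer taken today, on a form to be completed before any allowed medication. Read literally, it covers today up to the time of completion.
- Item 12 asks about side effects after taking the product, on a form completed before the product. It must refer to an earlier interval.
- Items 1–8 carry neither anchor.

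The two anchors point to different periods, so a participant cannot infer which one applies to cough or congestion.

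**2. The plan's own figure.** Section 7.2: 200 enrolled × 0.40 with a cold = 80. This reproduces and is unaffected by the point. It supplies n = 80 below.

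**3. Simplest size calculation.** The documents give no rate of momentary answering, so the share q is an assumption. If a share q is recorded exactly one day early and nobody is censored, the shift in mean time to freedom is q × 1 day.

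| q (assumed) | Participants of 80 | Shift in mean |
|---|---|---|
| 0 | 0 | 0 |
| 0.25 | 20 | 0.25 day |
| 0.50 | 40 | 0.50 day |

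Simulated medians fall on average by nearly the same amount: about 0.24 day at 25% and 0.48 day at 50%. This is the assumption restated, not evidence. With whole-day diaries a median moves in steps. For n = 80 and log-normal durations (median 5 to 9 days, log-scale SD 0.4 to 0.6, no censoring), take the median as the day by which half have recovered. It is then unchanged in about 73–77% of simulated trials at q = 0.25 and 51–55% at q = 0.50. A convention that takes midpoints at ties would move more often.

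**4. A wider illustration.** Assume durations are log-normal with median 5, 7 or 9 days and log-scale SD 0.5. On each of the last 2 or 3 symptomatic days, assume a 10% to 30% chance that the pre-dose diary reads all zero. The first all-zero entry counts as the event, and time is capped at 18 days.

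| Setting | Colds ended early | Of 80 | Loss in mean within 18 days |
|---|---|---|---|
| 0% chance | 0% | 0 | 0 |
| 10%, last 2 days | about 19% | 15 | 0.27–0.28 day |
| 30%, last 3 days | 63–65% | 50–52 | 1.34–1.40 days |

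Across the settings the whole-day median moves by 0 to 2 days. These figures reflect the missing window and the missing confirmation rule together.

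**5. Compared with precision.** The approximate 95% half-width for a median m is 1.96 × 0.5 / (f√n), where f = 1/(m × 0.5 × √(2π)) is the log-normal density at the median. For m = 7, f = 1/(7 × 0.5 × 2.507) = 0.114, and the half-width is 1.96 × 0.5/(0.114 × 8.944) = 0.96 day. For m = 5 and m = 9 it is 0.69 and 1.24 days. A bias of 0.25 to 0.5 day lies inside that range, while the upper end of step 4 reaches or passes it. Step 4 concerns a mean and this step a median, so only the order of magnitude is comparable.

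**The case against.** Several counter-arguments have force.

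- **No document says that one all-zero diary is the event or ends follow-up.** Exit follows resolution of all symptoms, and section 6.1 also has temperature recorded in the diary, so the event may not rest on the eight items alone. This stands: the claim is that the plan permits the error, not that it prescribes it. The diary marked at study exit in section 6.2 does not close the gap, because exit itself falls at resolution.
- **Much of the harm comes from the absent confirmation rule and exit at resolution.** This stands in part. A recall window would make an all-zero entry cover a day instead of a moment, but it would not detect relapse afterwards.
- **The magnitude is assumed.** This stands in full.
- **The study is single-arm and descriptive, and section 11 discloses its reliance on self-report.** This limits the consequences. Disclosing subjectivity does not define the question being asked, however, and the comparison with published durations will still be read.

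A reader might also infer from the printed form that paper diaries cannot be placed on the time axis, or that a late upload date would become the event date. The documents do not support this. None of the forms in Appendices C to G shows a date or identifier line, so the appendix may list question content only. The portal and eDiary are the main route, paper is meant for real-time use, the cold start form is not shown, and no upload date is mentioned anywhere. What remains is that the plan does not say how a paper entry gets its date, although section 7.3 relies on report dates.

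**Conclusion.** The point holds in limited form. Items 1–8 lack a recall period, the form is completed once a day before the product, and nothing in the endpoint definition or exit rule would correct an entry that captured only a quiet moment. Any resulting error shortens the recorded cold relative to a past-day rating.

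Its size is unknown. It is zero if nobody answers for the moment, and about the share doing so times one day if each is one day early. The 0.3 to 1.4 day range depends on assumed duration and diary patterns and also includes the missing confirmation rule, so it should not be quoted as an estimate of this defect alone.

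The paper-diary dating question is a request for clarification, not a demonstrated flaw. The change is worth making before first use because the missing window cannot be reconstructed later.

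**What to change.** 1. **Stem of items 1–8.** Use a fixed window, for example: 'In the past 24 hours, how bad was this symptom at its worst?' The first diary should instead rate symptoms since onset. A fixed window is preferable to one running from the previous entry, which has no anchor on the first diary and stretches after a missed day.
2. **Paper diary (minor).** Add an assessment date, and state in section 7.3 that event and censoring times use that date.

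The cost is an edit to one form and a sentence in section 7.3. The downside is that recovery is recorded up to about a day later and recall is slightly longer. The window should be reported beside the published results, whose own windows may differ. Relapse after exit needs a separate sustained-resolution rule; this edit does not replace it.
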